Short Title	HNSCC Audit 2023
Study Leads	INTEGRATE Head & Neck Subspecialty Committee
Study Design	Multi-centre retrospective national audit
Study Participants	Patients >18 year old with confirmed mucosal squamous cell carcinoma of the head and neck
Planned Sample Size	No a priori calculation
Follow-up duration	2 years
Planned study period	1st September to 30th November 2021
Aim	To assess current real-world management of HNSCC in the UK
Primary Objectives	 To gain a large-scale understanding of the management decisions of patients with HNSCC discussed at MDT in the UK a. by collecting patient demographics and HNSCC disease data b. by collecting MDT recommendations To assess this management for adherence to national guidelines
Secondary Objectives	 To gain an understanding of the variation in HN MDT recommendations To evaluate the 2-year overall, disease-specific and disease-free survival outcomes, and recurrence rates of head and neck cancers To audit UK-wide HNSCC pathways and their compliance with cancer waiting targets, including identifying delays and potential areas for improvement 28 days 'Faster Diagnosis Standard' (FDS) for primary HNSCC 31 days from the referral to decision-to-treat 62 days from referral to the commencement of treatment (31 days for recurrent HNSCC) To examine the use of local anaesthetic biopsy for histological diagnosis and its impact on pathway timings To assess the HN MDT workforce against national guidelines
Methods	Identify patients with HNSCC discussed at HN MDT within the study period. Central submission of anonymised cases for pooled analysis.

4 Background

Head and Neck cancers are the seventh most common cancer globally, with a prevalence of 4.1 million cases reported in 2016 (1). The term encompasses a diverse, heterogeneous group of pathologies that can affect multiple anatomical regions and interact with several important physiological systems. In addition, 60-70% of HN cancer patients present with locally or regionally advanced disease, making multimodal management a necessity (2). As such, managing HN cancers can be complex and well-suited for a MDT approach (2). This involves collaboration and discussion between multiple different medical specialities to improve patient care, including Ear, Nose and Throat (ENT), Oral and Maxillofacial Surgeons (OMFS), Plastic Surgeons, Oncologists, Radiologists, Pathologists, Oncology Nurses, Dietitians and Speech and Language Therapists.

The MDT concept emerged in the 1980s when it was found surgery with post-operative chemotherapy or radiotherapy improved outcomes in patients diagnosed with cancer (3). In the 1990s and early 2000s, several retrospective studies demonstrated that MDT approaches improved survival rates for cancer patients and positively affected treatment decisions (4–6). For HN cancers, a meta-analysis conducted by Shang et al demonstrated that patients managed via an MDT approach had a higher survival rate (HR = 0.84, 95% CI (0.76-0.92), P = 0.0004) (7). MDTs were also found to improve adherence to evidence-based guidelines and to improve efficiency in care (8,9). A retrospective audit conducted by Kelly et al (10) found that MDT discussion improved rates of pre-operative nutritional assessments (57% vs. 39%), PET-CT staging (41% vs. 2%) and reduced the interval between surgery and radiotherapy for patients with head and neck cancer. These clear benefits have resulted in the MDT being widely adopted throughout the world in cancer management.

In the United Kingdom, the guidelines for decision-making in the management and preoperative workup of HN Cancers are provided by the National Institute for Health and Care Excellence (NICE) (11). Outside these guidelines, general recommendations for running an effective MDT include strong leadership to help guide decision-making (2,12–14), the importance of good record-keeping (12,14) the inclusion of allied healthcare professionals such as Speech and Language Therapy to help with supportive interventions (3) and the importance of a specialist oncology nurse to act as a point of contact between the team and the patient (2,3,12).

The British Association of Head and Neck Oncologists (BAHNO) produced their first guideline on the management of HN cancers in 2002. In 2020 it published its most recent guideline "British Association of Head and Neck Oncologists (BAHNO) standards 2020" (15), which set out to establish standards for HN MDTs UK-wide, as well as encourage sharing of knowledge between different MDTs. Anecdotally there is variation in practice amongst MDTs throughout the country, with some more oncologically-orientated and others more surgically-orientated. Standardising HN MDTs is difficult due to regional variation in resources and demographic characteristics. As such, this protocol outlines a national retrospective audit to understand the decision-making process for patients with HN cancer across the United Kingdom, focusing specifically on HNSCC that comprises the majority of diagnoses.

5 Aim and objectives

5.1 Aim

1. To define the current management of primary and recurrent mucosal HNSCC in the UK.

5.2 Primary Objectives

- 1. To gain a large-scale understanding of the management decisions of patients with HNSCC discussed at MDT in the UK
 - a. by collecting patient demographics and HNSCC disease data
 - b. by collecting MDT recommendations
- 2. To assess this management for adherence to national guidelines

5.3 Secondary Objectives

- 1. To gain an understanding of the variation in HN MDT recommendations
- 2. To evaluate the 2-year overall, disease-specific and disease-free survival outcomes, and recurrence rates of head and neck cancers
- 3. To audit UK-wide HNSCC pathways and their compliance with cancer waiting targets, including identifying delays and potential areas for improvement
 - a. 28 days 'Faster Diagnosis Standard' (FDS) for primary HNSCC
 - b. 31 days from the referral to decision-to-treat
 - c. 62 days from referral to the commencement of treatment (31 days for recurrent HNSCC)
- 4. To examine the use of local anaesthetic biopsy for histological diagnosis and its impact on pathway timings
- 5. To assess the HN MDT workforce against national guidelines

6 Study design and setting

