8.6 Dataset

The full dataset is delineated in the study Excel Data Tool. This tool will collect data in the following areas:

- Demographics and referral details: demographics; smoking status; alcohol status; ECOG performance status; source of referral
- MDT details: unit type (tertiary referral or district general); frequency of MDT; platform; same-day clinic; specialties present; allied healthcare professionals
- Cancer pathway dates: date of referral; date of first specialist clinic; date of biopsy; date of MDT outcome; date patient was informed of diagnosis; date treatment commenced; FDS
- Diagnostic biopsies: date of biopsy(s); subsite(s); anaesthesia; location (clinic or operating theatre)
- Imaging for diagnosis: modality, body site
- Diagnosis: subsite; clinical T stage; clinical N stage; clinical M stage; TNM 8; new or recurrence; p16 and HPV status; EBV status; PDL-1 status; presence of clinical ENE; presence of synchronous head and neck tumour
- Presence of synchronous HNSCC: subsite; clinical T stage; TNM 8; new or recurrence; p16 and HPV status; EBV status; PDL-1 status
- **Treatment:** modality of treatment (including surgical and/or oncological technique, timings or doses); treatment intent
- **Recurrence:** recurrent or residual disease; nature of recurrence (local, regional or distant); timing of recurrence after completion of treatment; treatment of recurrence
- Surveillance: timing of post-treatment surveillance imaging; modality
- Follow-up: time to last follow-up and/or death; cause of death

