10.3 Sub-group analysis

Sub-group analysis may include, but not be limited to:

- Patients with primary and recurrent HNSCCs, respectively
- Patients with HPV-positive and negative oropharyngeal tumours, respectively, confirmed via p16 immunocytochemistry or fluorescent in-situ hybridisation
- Patients with a histologically confirmed primary HNSCC with an N3 neck nodal staging
- Patients with a histologically confirmed primary or recurrent HNSCC and an additional synchronous primary or recurrent HNSCC
- Patients with a histologically confirmed primary HNSCC who had diagnostic biopsy performed under local anaesthetic in the outpatient clinic

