10.5 Statistical analysis

Patient demographic data will be presented with mean and SD for continuous variables and counts and proportions for categorical variables. Categorical data will be analysed with the Chi-square or Fisher's Exact test as appropriate. Quantitative continuous variables will be analysed using descriptive statistics such as

mean, standard deviation, median, quartiles, minimum/maximum and range. Continuous variables will be assessed with Student's t-test, Mann-Whitney U test, Kruskal-Wallisor the Wilcoxon test as appropriate.

Survival curves will be produced using the Kaplan-Meier method. Sensitivity analyses will be undertaken. Comparison of survival outcomes for sub-groups will be performed using the log rank test and Cox Proportional Hazard model.

11 Ethical considerations

This audit will report on the outcomes of investigative management that has already taken place. There will be no effect on the management of patients as a result of inclusion in the study. All data will be anonymised, and no patients will be identifiable in any subsequent reports, presentations or publications. As such, consent from individual patients will not be required.

This project has been determined to be an audit using the HRA decision tool available at http://www.hra-decisiontools.org.uk/research/ (Appendix 1). The output from this process is available in the Appendix. This should be discussed locally for study participation approval on request.

Local centres are asked to register the audit with their audit department and/or Caldicott guardian, in keeping with local protocol.

12 Authorship policy

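### The objective on the impact of local anaesthetic biopsy on pathway timings is matched only by unadjusted tests and an ambiguous subgroup, so the contrast can be biased by subsite and by how failed attempts are classed

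*Protocol*

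**What the plan says.** Section 5.3 lists as a secondary objective: "To examine the use of local anaesthetic biopsy for histological diagnosis and its impact on pathway timings". It names neither a comparator nor an interval.

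The only subgroup that matches is in section 10.3: "Patients with a histologically confirmed primary HNSCC who had diagnostic biopsy performed under local anaesthetic in the outpatient clinic". The list it belongs to is optional and open-ended: "Sub-group analysis may include, but not be limited to".

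On tests, section 10.5 states: "Continuous variables will be assessed with Student's t-test, Mann-Whitney U test, Kruskal-Wallisor the Wilcoxon test as appropriate". For categorical data, such as a waiting target met or missed, it states: "Categorical data will be analysed with the Chi-square or Fisher's Exact test as appropriate". The Cox model appears only for survival outcomes. Sensitivity analyses are promised in the same survival paragraph, without content.

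The dataset in section 8.6 collects, under diagnostic biopsies, "date of biopsy(s); subsite(s); anaesthesia; location (clinic or operating theatre"). It also lists tumour subsite, T and N stage, ECOG performance status, referral source and the pathway dates. It lists no field for whether a biopsy was adequate, and no rule says how a patient with more than one biopsy is classed.

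**The concern.** Two separate mechanisms can distort the comparison.

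- **Subsite.** Section 7.1 admits six subsites, from oral cavity to hypopharynx and larynx. They plausibly differ both in how readily they can be biopsied in clinic and in how long the pathway takes. An unadjusted test of LA against other routes then partly compares subsites.
- **Classification.** If the group is set by the biopsy that yielded the diagnosis, a patient whose LA biopsy failed and who then had another biopsy in theatre falls into the comparator and takes the delay there. Delay caused by the LA route is charged to the alternative.

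The subgroup is also narrower than the objective. Anaesthesia and location are separate fields, so an LA biopsy in theatre is possible, yet it falls outside the subgroup.

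At stake is a published statement about days saved or lost by LA biopsy that could reflect case mix and classification rather than biopsy route.

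**Working it through.** The protocol gives no effect size, sample size, LA uptake, failure rate or interval by subsite for this objective, so there is no figure of its own to reproduce. Every input below is an assumption, used to show mechanism and scale.

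**Inputs (assumed).** Accessible subsites make up 60% of patients, of whom 70% have LA first; less accessible subsites make up 40%, of whom 15% have LA first. The pathway is d = 7 days longer at less accessible subsites. LA brings no benefit. A failed LA attempt adds 14 days, and 20% fail in both strata.

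**Step 1: subsite alone.**
- LA first: 0.60×0.70 + 0.40×0.15 = 0.42 + 0.06 = 0.48. Other: 0.18 + 0.34 = 0.52.
- Less accessible share: other 0.34/0.52 = 0.654; LA 0.06/0.48 = 0.125.
- Bias = 7 × (0.654 − 0.125) = 3.7 days in favour of LA.
- Range, sign of d held: uptake 60%/30% with d = 5 gives 5 × (0.28/0.52 − 0.12/0.48) = 1.4; uptake 80%/10% with d = 10 gives 10 × (0.36/0.48 − 0.04/0.52) = 6.7.
- With d = −7 the result is 3.7 days against LA.

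**Step 2: add classing by the successful biopsy.**
- Failures moved: 0.48 × 0.20 = 0.096, so the comparator becomes 0.52 + 0.096 = 0.616.
- Delay carried in: 14 × 0.096/0.616 = 2.18 days.
- The moved patients are mostly at accessible subsites, so the comparator's less accessible share falls to (0.34 + 0.012)/0.616 = 0.571, worth 7 × 0.571 = 4.00 days.
- Comparator excess: 4.00 + 2.18 = 6.18, against 7 × 0.654 = 4.58 before, a rise of 1.6 days.
- LA group: 7 × 0.125 = 0.88. Contrast: 6.18 − 0.88 = 5.3 days in favour of LA. The two mechanisms do not simply add (3.7 + 2.2 would be 5.9).

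**Step 3: what each remedy does.** By construction, trying LA first costs 0.20 × 14 = 2.8 days on average. LA minus other, in days (negative favours LA):

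| Analysis | d = +7 | d = 0 | d = −7 |
|---|---|---|---|
| Crude, by successful biopsy | −5.3 | −2.2 | +0.9 |
| Crude, by first attempt | −0.9 | +2.8 | +6.5 |
| Within subsite, by successful biopsy | −2.9 | −2.9 | −2.9 |
| Within subsite, by first attempt | +2.8 | +2.8 | +2.8 |

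Row 1 is 2.18 + d × (0.571 − 0.125), with the sign changed. Row 2 is 2.8 − d × 0.529. Row 3 is 0.6 × 14×0.084/0.264 + 0.4 × 14×0.012/0.352 = 2.67 + 0.19, with the sign changed. Only row 4 returns the built-in value throughout, so both changes are needed.

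**Step 4: simulation with different assumed inputs** (half at accessible subsites, LA uptake 70%/20%, SD 20 days, the same 14-day penalty). Crude LA minus other differences at 0%, 10% and 20% failure:
- d = +7: −3.6, −4.4, −4.9 days. With 500 patients, Mann-Whitney p<0.05 in 47%, 62% and 73% of runs.
- d = 0: 0.0, −1.1, −2.0 days.
- d = −7: +3.6, +2.2, +1.1 days.

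The classification effect always moves the contrast towards LA; the subsite effect takes the sign of d.

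**The case against.** The strongest reply is that this is analysis-plan detail. Covariates, the main interval and the handling of repeat biopsies usually sit in a SAP, which may exist and is not shown. Section 10.5 lists tests to be used as appropriate and does not forbid stratification. The section 10.3 subgroup is optional, has no stated comparator, and is not declared to be the way objective 4 will be answered. This is one secondary objective in a descriptive audit, and *impact* may be loose wording.

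Part of that stands. A missing covariate list alone would not be a finding. But the protocol does state a firm objective about impact, does name the tests for continuous and categorical data, and does confine its only regression model to survival. Followed as written, it gives an unadjusted contrast.

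A reader might go further and infer that the plan will produce a spurious LA benefit. The documents do not support that:
- The direction of the subsite bias rests on an assumed difference, and reversing it reverses the bias.
- Nothing in the protocol says that failed LA attempts move to the comparator.
- A diagnostic biopsy can also mean any biopsy taken for diagnosis, and section 8.6 allows several per patient under that label.
- The tests are not limited to two groups, since Kruskal-Wallis is listed.

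**Conclusion.** The concern holds in a limited form. The protocol sets out to examine impact, names only unadjusted tests for the timings, and offers one matching subgroup that omits LA biopsies in theatre and is ambiguous about failed attempts. The resulting contrast can be biased by subsite in either direction. It is shifted towards LA if patients are classed by the successful biopsy and failures cost time.

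The worked sizes, 3.7 days from subsite alone and 5.3 days with both mechanisms, illustrate scale under assumed inputs; they do not predict what this audit will find. With no subsite difference and no failed attempts, the bias from these two sources is zero. The point merits a change because a better analysis is available largely from fields already listed, but it affects one secondary objective and not the audit's primary aims.

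**What to change.** - Class patients by anaesthesia at the first biopsy attempt, whatever the location, so that failed LA attempts stay in the LA group. This needs no adequacy field. Confirm that the Excel Data Tool records anaesthesia separately for each biopsy; section 8.6 does not make this clear.
- Define diagnostic biopsy in section 10.3, and align the subgroup with the objective on LA biopsies done in theatre.
- Compare intervals and target compliance stratified by, or adjusted for, subsite, and also for stage, ECOG status and coded centre where numbers allow. Show results within subsite.
- Name the comparator and the main interval, and report the result as an association. If no adjusted analysis is intended, reword objective 4 as descriptive.

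**Cost.** Mostly wording, one check of the data tool and slightly more analysis work. The estimate will be less precise, and any apparent LA benefit may turn out smaller. Residual confounding by factors that are not recorded will remain.

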6.1 Study design

Retrospective multi-centre observational audit of practice.

6.2 Study setting

UK secondary or tertiary centres investigating and treating HNSCC.

7 Patient eligibility criteria

7.1 Inclusion criteria

- 18 years and older
- Patients with a new or recurrent histologically diagnosed primary mucosal HNSCC (non-cutaneous) of one of the following subsites:
 - Oral cavity
 - Oropharynx
 - Nasopharynx
 - Sinonasal cavity
 - Hypopharynx
 - Larynx
- Patients who underwent discussion at a HN MDT, with a complete and final MDT treatment recommendation made between 1st September 2021 and 30th November 2021

7.2 Exclusion criteria

- Patients under 18 years old
- Patients with a primary HN cancer of thyroid, cutaneous, salivary gland, lateral skull base, or non-squamous cell origin
- Patients with an HNSCC of unknown primary
- Patients with a diagnosis of dysplasia, or carcinoma-in-situ

8 Study procedures and methodology

8.1 Project registration

This is a local investigator-led, non-commercial, non-interventional national audit of clinical practice. No patient identifiable information will be collected by the PMT and data analysis will not identify hospitals individually. As such, the anticipated risks to patient confidentiality are extremely low.

The project must be registered with local Clinical Governance Departments responsible for the conduct of local audit prior to submission of any data to the PMT.

8.2 Patient identification

Local investigators will obtain a list of consecutive patients from their centres for inclusion into the study.

These patients will:

have had a diagnosis of primary or recurrent HNSCC

AND

- have been discussed at MDT

AND

- have had a definitive 'decision to treat' for their primary or recurrent HNSCC documented via their MDT outcome between 1st September 2021 and 30th November 2021.

Local investigators are advised to acquire patient lists via their H&N MDT co-ordinators. Where a patient list is obtained via an MDT coordinator, it is recommended that the list is limited to the most recent discussion date for each patient, so that final MDT outcomes can be retrieved following investigations. 2-year follow-ups for these patients will then be retrieved by local investigators where available.

Where necessary, the PMT will be able to further guide local investigators upon request: [contact]

The MDT notes and 2-year outcomes for all patients will be reviewed by the local team and full eligibility criteria applied. All eligible patients will be recorded onto an Excel Data Tool. All screened patients and any reasons for exclusions will be recorded.

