8.8 Anticipated numbers/workload

Activity	Cohort	Anticipated numbers for mid-large MDT discussing 10-20 patients / week and diagnosing 200 SCC /yr
Initial identification	Patients discussed at MDT	- up to 200 / 3-month period / unit
Eligibility criteria	New or recurrent histologically confirmed HNSCC	- up to 50 / 3-month period / unit
Data collection	Documented MDT outcome between 1st September, 2021 and 30th November, 2021	- up to 50 / 3-month period / unit
	2 years of follow-up date available	- up to 50 / 3-month period / unit

9 Data Management

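### Sections 7.1 and 8.2 define cohort entry in different, undefined terms, so sites may or may not include patients whose final MDT outcome is no active treatment

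*Protocol*

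**What the plan says.** Section 7.1 (Inclusion criteria) takes adults with histologically diagnosed mucosal HNSCC, new or recurrent, who were discussed at a head and neck MDT "with a complete and final MDT treatment recommendation made between 1st September 2021 and 30th November 2021".

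Section 8.2 (Patient identification) describes the consecutive list that each site draws up. It sets three conditions joined by AND: a diagnosis of HNSCC, discussion at MDT, and that patients "have had a definitive 'decision to treat' for their primary or recurrent HNSCC documented via their MDT outcome" within the same dates. It then says that the MDT notes and 2-year outcomes "will be reviewed by the local team and full eligibility criteria applied", and adds: "All screened patients and any reasons for exclusions will be recorded".

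Section 8.8, a workload table, labels its data-collection row "Documented MDT outcome between 1st September, 2021 and 30th November, 2021".

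None of the four exclusions in 7.2 concerns best supportive care or no active treatment. The first primary objective (5.2) is "To gain a large-scale understanding of the management decisions of patients with HNSCC discussed at MDT in the UK". The second secondary objective (5.3) is "To evaluate the 2-year overall, disease-specific and disease-free survival outcomes, and recurrence rates of head and neck cancers". The only other use of the term decision-to-treat is in 5.3, as a waiting-time milestone at 31 days from referral, and it is not defined there either.

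**The concern.** A final MDT recommendation and a decision to treat are the same event for a patient who goes on to surgery or radiotherapy. They may differ for a patient whose MDT concludes that no active treatment should be given. That patient has a final MDT outcome, but on a literal reading has no decision to treat. If a site applies 8.2 in that sense, it selects patients on the content of the management decision, which is what the primary objective sets out to describe.

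Three results could be affected:

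- the share of patients managed without active treatment, which would be under-reported;
- the variation in MDT recommendations (first secondary objective), part of which would reflect how each site read the entry rule;
- pooled 2-year overall and disease-specific survival, which would be too high if the omitted patients survive less well.

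A patient missing from the list cannot be recovered at analysis. The protocol states that the central database cannot be traced back to local records. The dates listed in 8.6 include the MDT outcome but no decision-to-treat date, so those fields would not show which reading a site used.

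**Working it through.** The protocol states no figure on this point and has no sample size calculation, so there is nothing to reproduce. The check is a comparison of the text, followed by an illustration on assumed inputs.

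**Text.** Take a patient with confirmed laryngeal SCC whose final MDT outcome in October 2021 is best supportive care.

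| Place | Entry condition | Does this patient enter? |
|---|---|---|
| 7.1 | final treatment recommendation | Unclear: depends on whether a recommendation against active treatment counts |
| 8.2 | definitive decision to treat | No on a literal reading; yes if the term means any final MDT outcome |
| 7.2 | four exclusions | Not excluded |
| 8.8 (workload label only) | documented MDT outcome | Yes |

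No section settles the two uncertain rows, so two careful sites can reach opposite answers.

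**What 8.8 suggests about intent.** The reference unit diagnoses 200 SCC a year, and 200 / 4 = 50 per three months. The table carries up to 50 unchanged from confirmed HNSCC to documented MDT outcome. These are upper bounds, but they show no planned loss of patients without active treatment.

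**Illustrative size.** Let q be the share of eligible patients with a no-active-treatment outcome, S_t the 2-year overall survival of the rest, and S_u that of the no-active-treatment group. None of these comes from the protocol.

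- Survival with everyone included: (1 − q) × S_t + q × S_u
- Survival with the group left out: S_t
- Overstatement: S_t − [(1 − q) × S_t + q × S_u] = q × (S_t − S_u)

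Assume S_t = 70% and S_u = 5%:

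| q | All included | Left out | Overstatement (points) |
|---|---|---|---|
| 5% | 0.95 × 70 + 0.05 × 5 = 66.75% | 70% | 0.05 × 65 = 3.25 |
| 10% | 0.90 × 70 + 0.10 × 5 = 63.5% | 70% | 0.10 × 65 = 6.5 |
| 15% | 0.85 × 70 + 0.15 × 5 = 60.25% | 70% | 0.15 × 65 = 9.75 |

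Over a wider grid (q from 2% to 15%, S_t from 60% to 80%, S_u from 0% to 10%) the overstatement runs from 0.02 × (60 − 10) = 1.0 to 0.15 × (80 − 0) = 12.0 points.

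All these values suppose that every site leaves the group out. If every site includes it, the overstatement is zero. If sites differ, the pooled figure lies in between.

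**The case against.** The strongest reply is that the two phrases mean the same thing. Section 8.2 ties its phrase to the MDT outcome, uses the same dates as 7.1, and goes on to give the retrieval of final MDT outcomes as the purpose of the list. It recommends a coordinator list limited by each patient's latest discussion date, not by treatment decision. Section 8.8 likewise starts from everyone discussed at MDT. Local teams then apply the full criteria and log exclusions, and the central team offers guidance. The Excel Data Tool is not shown and may already code these outcomes.

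Much of this stands. It rules out several stronger readings that a reader might infer:

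- *That these patients are certainly excluded and survival is certainly biased.* No section says so. The equivalent reading is open, and under it there is no bias.
- *That three eligibility rules compete.* Section 8.8 is a planning table, and its label is shorthand. Only 7.1 and 8.2 set conditions, and the wording of 7.1 is itself ambiguous for these patients.
- *That survival comparisons between MDTs would be distorted.* None is planned. Section 10.2 pools all cases, and the objective on variation concerns recommendations.
- *That patients who decline treatment are lost in the same way.* If the MDT recommended treatment and the patient later refused, the documented outcome stands and the patient can meet both sections.

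The reply does not remove the ambiguity. The decision-to-treat condition is part of 8.2's description of who is listed, and the protocol's only other use of the term is as a pathway milestone ahead of the start of treatment, which favours the narrow sense. The log covers screened patients. It would show a removal made at review, but not an omission made when the list was drawn, and applying 7.1 afterwards cannot restore someone never listed.

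**Conclusion.** The point holds as an inconsistency in the entry rule that carries a risk of selection bias. It does not show that bias will occur. Sections 7.1 and 8.2 use different terms, neither is defined for a patient given no active treatment, and the literal reading of 8.2 is narrower than the primary objective requires.

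Any error in pooled overall survival would be upward, provided that patients without active treatment survive less well than the rest. Its size cannot be known from the protocol. It is zero if sites treat these outcomes as decisions to treat, and reaches about 10 percentage points if all sites leave the patients out and the assumed 15%, 70% and 5% apply. Disease-specific survival would move in the same direction if the omitted patients die of their cancer more often, but nothing in the protocol allows that to be sized.

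This cannot be left to the analysis plan, because eligibility is applied by sites before any analysis.

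**What to change.** Use one entry event in 7.1 and 8.2, and match the label in 8.8: a final MDT management outcome documented between 1 September and 30 November 2021, whatever its content. State explicitly that best supportive care and no active treatment are included.

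Keep these patients in the primary objective and in overall and disease-specific survival. Use the term decision to treat, with a definition, only for the waiting-time standards. Check that the Excel Data Tool has a code for these outcomes, and send sites a short note so that lists already drawn can be rechecked.

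The cost is one sentence aligned across the sections, the note to sites, and a few more records per site, all for patients already on the MDT list. At the table's ceiling of 50 per unit, the assumed 5% to 15% is 50 × 0.05 = 2.5 to 50 × 0.15 = 7.5 records. Reported survival may be slightly less favourable, but it will describe the population named in the primary objective.
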